9.1 Study committees

9.1.1 Study Management Group (SMG)

The Study Management Group is set up for this study. It consists of the EORTC Headquarters team in charge of running the study (clinical research physician, statistician, clinical scientist, clinical operations manager and data managers) and the principal study coordinator.

The EORTC Headquarter team, in collaboration with AbbVie, is responsible for the day -to-day conduct of the trial. The Study Coordinator will assist the team in case of problems with patient evaluation (eligibility, treatment compliance, safety).

The Study management Group also performs the medical review as indicated below.

9.1.2 Study Steering committee (SSC)

The Study Steering Committee for this study is composed of the study coordinators, the representatives of Academic Groups collaborating to the study, at least one representative of the EORTC Headquarters (Study Clinical Research Physician or Clinical Scientist) and one representative of the Sponsor, if the sponsor is not the EORTC.

This committee provides the general oversight of the study and has the executive power. The SSC monitors study progress and conduct and advises on its scientific credibility. The SSC will consider and act, as appropriate, upon the recommendations of the independent data monitoring committee.

9.1.3 Independent data monitoring committee (IDMC)

The independent data monitoring committee for EORTC studies (IDMC) is in charge of the independent oversight of this study. The composition of the IDMC is described in EORTC Policy "Independent Data Monitoring Committees for EORTC studies" (ref. EORTC POL004) and its functioning is ruled by the charter annexed to the Policy.

The study-specific experts on the IDMC performing this review will be selected for their relevant expertise with the disease and/or treatments assessed in the study.

The IDMC reports its recommendations in writing to the Study Management Group through the clinical operations manager to the Study Steering Committee and other relevant parties (supporting bodies, collaborative groups...).

9.2 Data Monitoring

9.2.1 Monitoring during medical review meetings

The medical review will be performed on a regular basis by the clinical research physician assisted as needed by the study management group. The main study coordinator will, in particular, support the Study Clinical Research Physician during the medical review process and will assist the team in case of problems with patient evaluation (safety, eligibility, treatment compliance). The main study coordinator is also responsible for the review and approval of the medical review plan and medical review reports.

For blinded trials, the medical review is conducted blinded to treatment allocation.

If at any time during the course of the study, the medical review identifies safety signals or other elements that could affect the potential risks and benefits to the study participants. These will be reported to the Study Steering Committee and may trigger a review by the EORTC Independent Data Monitoring Committee (IDMC) as well as the collaborative partner (AbbVie).

9.2.2 Monitoring by the IDMC

The IDMC will be asked to give advice on whether the accumulating data from the trial justifies continuing recruitment of further patients or further follow-up.

The IDMC will review the trial whenever safety problems or other elements are identified during the medical review or by the SMG and/or SSC that could affect the potential risks and benefits for study participants.

The IDMC will also review the intermediate reports of accumulating data according to the study interim monitoring plan described in the statistical section of this protocol. If a decision is made to continue without change, the IDMC may advise on the frequency of future reviews of the data on the basis of accrual and event rates.

While the trial is ongoing the accumulating data will generally remain confidential, unless the SSC and IDMC agree that the data should be made public.

10 Quality of Life assessment

10.1 Rationale

Health related quality of life (HRQoL) is a multidimensional construct, which can be defined as a state of general wellbeing reflecting physical, psychological, and social wellbeing and the impact of the disease and/or treatment related symptoms on daily-life functioning. The patient's subjective perspective is an inherent component of HRQoL and is therefore best assessed via self-administration.

Reducing mortality and morbidity is still the most important factor in cancer clinical research.

Nevertheless, issues such as reducing side effects, symptom relief and improving patients' satisfaction have also become relevant parameters in the evaluation of medical strategies. Cancer treatments may produce adverse effects and diminish a patient's quality of life even when survival is extended. Progress in the acceptance of new cancer therapies is sometimes critically dependent on their HRQoL consequences.

10.2 Objective

The current experience with angiogenesis inhibiting agents in recurrent GBM has demonstrated considerable difficulties with assessing response and progression in previously treated patients. So, we hypothesize that measures of clinical functioning will yield information (HRQoL, need for steroids, cognitive functioning) that is critical for the patient perception of clinical benefit.

The study hypothesis is that ABT-414 alone or in combination with TMZ improves overall survival compared to lomustine or TMZ single agent. In the present study, HRQOL is an exploratory endpoint. The main objective of HRQOL assessment within this trial is to determine the impact of ABT-414 on **overall global health and HRQoL**. A secondary objective is to evaluate the effect of the treatment on the remaining symptoms and functioning scales as treatment-related side effects may have a (temporary) negative influence on the health related domains of HRQOL of these patients.

10.3 HRQoL instrument

Quality of life will be assessed with the EORTC Quality of Life Questionnaire (QLQ-C30) version 3. This is composed of multi-item and single scales. These include five functional scales (physical, role, emotional, social, and cognitive), three symptoms (fatigue, nausea and vomiting and pain) and a global health status/HRQoL scale and six single items (dyspnea, insomnia, appetite loss, constipation, diarrhea and financial difficulties). All scales and single items meet the standards for reliability. The reliability and validity of the questionnaire is highly consistent across different language-cultural groups (Ref. 32). While this standard is used in EORTC studies, it lacks some dimensions that pertain to the QL issues in certain brain cancer. Therefore, we will use the EORTC Brain Cancer module (QLQ-BN20), designed for use in patients undergoing protocol treatment or radiotherapy. It includes 20 items assessing visual disorders, motor dysfunction, communication deficit, future uncertainty, as well as other specific symptoms, such as headaches, seizures or drowsiness. A retrospective validation study has been performed confirming the psychometric validity of this questionnaire (Ref. 33).

10.4 Study design

Patients are eligible for the quality of life assessment in this study if they fulfill the eligibility criteria (Chapter 3). Should the HRQoL forms not be available in the required language or should the patient refuse to fill out the form, then this should not exclude the patient from further participation in the study. Patients will be informed in the patient informed consent form that they will have their quality of life assessed regularly while involved in this trial. In this phase II trial, HRQoL will be an exploratory outcome and evaluated in a longitudinal design in all patients entered in this study.

HRQoL questionnaires must be filled out at the hospital when patients come for a scheduled visit according to the EORTC “Guidelines for administration of questionnaires” (see Appendix G). The pre-treatment questionnaires must be filled within 2 weeks before randomization. Subsequent questionnaires are administered at week 8 and 16 on-treatment, coinciding with the imaging visits. All patients are requested to complete a HRQoL assessment 6 months after randomization.

Master copies of the HRQoL questionnaires will be sent to the institutions. Additional copies or translations can be provided upon request via the EORTC contact person. The clinical report forms will include a question whether the HRQoL forms have been filled in, and if not, the reason why. The questionnaire will be handed out to the patients by the investigator or a study nurse prior to seeing the doctor for clinical evaluations. The patient should complete the questionnaires by her/himself in her/his own language during the visit as completely and accurately as possible. It is recommended that a key person (e.g. research nurse) at each center should be responsible for questionnaire data collection in order to optimize the compliance of the patient and to ensure the completeness of the data.

The time windows for eligible HRQoL assessments will be as follows:

Assessment	Time window
Baseline	For all patients. Can be completed before or on the day of randomization itself but no earlier than 2 weeks before.
Week 8 (on-treatment)	To be completed at the week 8 MRI visit while on protocol treatment.
Week 16 (on-treatment)	To be completed at the week 16 MRI visit while on protocol treatment.
At 6 months	For all patients. Can be completed at any time during the sixth and seventh month after date of randomization regardless of treatment or progression status.

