5.4 Withdrawal criteria

Whatever the disease status, study treatment will be discontinued in case of:

- ◆ disease progression
- ◆ patient refusal
- ◆ intolerable toxicity precluding further protocol therapy
- ◆ patient's best interest
- ◆ start of any other anti-cancer agent/modality (surgery at recurrence is allowed)
- ◆ pregnancy

Patients discontinuing therapy in the absence of progression should not receive other cancer treatment before their disease progresses, unless this is clearly not in the interest of the patient. If, after treatment discontinuation, there is additional clinical information leading the investigator to conclude that the reason for discontinuation is no longer valid (except for toxicity), the subject may resume study treatment as long as no other chemotherapy, radiotherapy, immunotherapy, NovoTTF, or other treatment with antineoplastic intent has been received, with the exception of surgical intervention that yields histology not demonstrative of tumor progression. In case of toxicity in the combination arm that is

clearly attributable to either TMZ or ABT-414, that drug can be discontinued and the other can be continued. Patients that discontinue study treatment for toxicity, patient refusal and other reasons remain 'on study' and must be followed according to the follow-up schedule for progression, survival etc unless patient specifically withdraws consent from all further data collection for the study (this decision should be clearly documented e.g in the medical notes).

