10.5 Statistical considerations

The primary HRQoL endpoint that is considered relevant for this study is the Global health/QoL status (GHQs) scale of the QLQ-C30 instrument. Other scales will be analyzed on an exploratory basis as secondary HRQoL endpoints, such as fatigue, communication deficit etc. The financial difficulties scale will not be analyzed.

The GHQs scale will be used as primary outcome of interest for this study. A change of 10 points on the 100-point QLQ-C30 scale will be considered as clinically relevant. The standard deviation of this scale is approximately 20 points. With the 2-sided alpha set at 5% and a power of 80% to detect a difference of 10 points (effect size of 0.5), a minimum of 128 patients (64 per treatment arm) is required. For an effect size of 0.75 (difference of 15 points), 56 patients (28 per treatment arm) are required. Therefore, this study is sufficiently powered to detect differences in HRQoL, although the emphasis is on establishing the magnitude and relevance of HRQoL differences rather than comparative tests.

Data will be scored according to the algorithm described in the EORTC scoring manual. All scales and single items are scored on categorical scales and linearly converted to 0-100 scales.

Changes in HRQoL scores per time point will be evaluated by classifying them according to the 10 point change threshold into 3 categories: improved, stable and deteriorated. Patients without a valid HRQoL outcome will be considered as having deteriorated. In case of discrete numbers (N<10), categories may be combined. The subsequent proportions will be compared between treatment arms using a chi-square test in the intent-to-treat population. In order to assess the robustness of the results, the following sensitivity analyses will be performed: a clinical relevant threshold of 5 and 15 points will be used and patients without a valid HRQoL score will be classified according to the reported reason for non-compliance.

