10.5.1 Missing data

Missing data is a potential major source of bias in HRQoL assessment.

In order to check the potential impact in the study, the compliance mechanism will be investigated prior to initiating the HRQoL analysis. Characteristics of patients with and without valid HRQoL data will be compared and trends over time per dropout pattern will be investigated. Model building will be used in order to investigate whether the compliance mechanism is linked to selected prognostic variables.

Once the main analysis is completed, sensitivity analyses will be undertaken to verify the robustness of the results vis-à-vis the missing data.

In case overall compliance is deemed too low (<50%), only an exploratory analysis will be performed in lieu of the main analysis.

11 Translational research

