- 5 ECG only Day 1 of Cycle 1 and 3, immediately after the ABT-414 infusion and only for subject treated with ABT-414 (Arm 1 or 2).
- 6 PK samples to be collected at Day 1 of ABT-414 Cycles 1, 2, 3 and then every 2 ABT-414 cycles (Day 5 samples will only be collected during Cycles 1 and 2).
- 7 Hematology at Day 21 can be omitted once treatment at the present dose level caused only grade 1 or less hem. toxicity at Day 21 and only grade 2 or less at Day 28.
- 8 QoL only at Week 8 and Week 16 while on treatment.
- 9 End of Treatment Visit 35 days after last protocol drug administration.
- 10 If clinically indicated/if clinically relevant.
- 11 Assessment of AEs not resolved after EOT or AEs related to study treatment.
- 12 PD samples to be collected at Day 1 of Cycles 1, 2 and 3 and only for subject in an ABT-414 arm (Arm 1 or 2).
- 13 PG sample optional, to be collected at Day 1 of Cycle 1 or it may be collected anytime during the study.
- 14 Repeat physical examination including WHO performance status and neurological evaluation, hematology, vital signs and adverse event assessments at Day 28 for subjects in the lomustine arm (Arm 3A).
- 15 Prophylactic steroid ophthalmic solution prior to each infusion of ABT-414; 2 drops in each eye every 8 hours to start 48 hours prior to ABT-414 dosing and continue for a total of 7 days.

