Compliance for a group of subjects at a certain time point T is defined as:

$$\text{Compliance (T)} = \frac{\text{Valid QoL form within [L, U]}}{\text{QoL form expected at T}}$$

Where L and U are the lower and upper bound of the time windows associated with T. The protocol schedule as specified in the protocol can be applied to this definition. The resulting values for T, L and U are summarized in [Table 6](#).

Table 6. Visit Window for QoL

	T	L	U	Window Length
Baseline	Date of randomization = D0	D0 – 1 week	D0	1 week
Week 8 (on-treatment)	Week 8 MRI visit date = D1	D1 – 1 week	D1 + 1 week	2 weeks
Week 16 (on-treatment)	Week 16 MRI visit date = D2	D2 – 1 week	D2 + 1 week	2 weeks
At 6 months	D0 + 6 months = D3	D3 – 30 days	D3 + 30 days	2 months

QoL forms are considered as invalid if either:

- All questions on the form are blank.
- The completion date is unknown or it cannot be assigned to a single assessment time point.
- The completion date falls outside all time windows.
- Multiple forms are received during the same time window. In the latter case, the form closest to the intended assessment time will be kept. In case of equidistance, the earlier form will be kept.

Forms are expected at T for each subject that was within the assessment window. A subject is considered to be within the assessment time window if at least one of the following conditions is met:

- At least one valid QoL form received within L and U
- Time on study > time from randomization till T

For the baseline assessment, all subjects are expected to have a completed QoL form.

The compliance rate between the arms will be compared at each post-baseline time point using a chi-square test. The following analyses will be presented per time-point:

- Compliance rate with QoL assessment by treatment group and overall
- Percentage of questions answered by treatment group (summary statistics)

- Comparison of compliance rates (chi-square test or fisher exact test (if expected cell frequencies are < 10))

In case significant differences are found, explanation of these differences should be sought and the analysis strategy adapted accordingly.

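### At weeks 8 and 16 the HRQoL form is offered only on protocol treatment, yet ITT patients without a form are scored as deteriorated

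*Protocol*

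**What the plan says.** **Collection.** Protocol 10.4 states "Subsequent questionnaires are administered at week 8 and 16 on-treatment, coinciding with the imaging visits". Its table of time windows says of the week 16 form: "To be completed at the week 16 MRI visit while on protocol treatment". Footnote 8 to the Protocol 6.5 summary table carries the same limit, and SAP Table 1 (section 4.2) repeats it: "QoL only at Week 8 and Week 16 while on treatment". The 6-month form follows the opposite rule: "Can be completed at any time during the sixth and seventh month after date of randomization regardless of treatment or progression status".

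**Scoring.** Protocol 10.5 sorts the change at each time point into improved, stable or deteriorated and compares the arms by chi-square in the ITT population, with the rule "Patients without a valid HRQoL outcome will be considered as having deteriorated". SAP 10.3 repeats both.

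**Denominator for compliance.** Under SAP 10.3 a form is expected if a valid one was received in the window or if "Time on study > time from randomization till T". For weeks 8 and 16, T is the MRI visit date (SAP Table 6). Protocol 5.4 says that patients who stop for toxicity, refusal or other reasons "remain 'on study' and must be followed according to the follow-up schedule for progression, survival etc". Protocol 6.4.1 continues the 8-weekly MRI after end of treatment, but only until progression.

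**Population.** An earlier paragraph of SAP 10.3 restricts all QoL analyses to ITT patients with at least one valid post-baseline form.

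**The concern.** Collection follows treatment status, expected forms follow time on study, and scoring follows randomization. These are three different sets of patients.

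The clearest case is the patient who stops for toxicity or refusal without progression. This patient is still on study and comes to the MRI visit, but the protocol says not to give the form. The SAP then counts the form as missing, and the three-category table records a deterioration that nobody measured. Patients who have progressed are also scored as deteriorated under the ITT rule.

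The stated HRQoL objective is the effect of ABT-414 on global health. At weeks 8 and 16 the three-category comparison mixes that effect with when and why patients stopped. The direction is not fixed: longer PFS on ABT-414 would favour ABT-414, while stopping for ABT-414 toxicity could reverse it.

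**Working it through.** **The plan's own figure.** For a 10-point difference, SD 20, two-sided 5% and 80% power: n = 2 × (1.96 + 0.84)² × (20/10)² ≈ 63 per arm, or 64 with the t distribution. For 15 points, n ≈ 28. Protocol 10.5 gives 64 and 28, so its sample size is reproduced and is not in dispute.

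**Inputs from the documents.** Median PFS 2.6 v 4.8 months (Protocol 8.3); median OS 7 v 12.9 months (Protocol 8.1.1); 240 patients randomized 1:1:1, so 80 per arm; 1 month = 30.4375 days (SAP 10.1).

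**Assumptions not in the documents.** Exponential times; treatment ends at progression and for no other reason; every requested form is returned; completers in both arms are 20% improved, 50% stable, 30% deteriorated (10/70/20 and 25/35/40 also tried).

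**Step 1: who has a form.** S(t) = 0.5^(t/median). Week 8 = 56/30.4375 = 1.84 months; week 16 = 112/30.4375 = 3.68 months.

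| | Control | ABT-414 |
|---|---|---|
| On treatment, week 8 | 0.5^(1.84/2.6) = 61.2% | 0.5^(1.84/4.8) = 76.7% |
| On treatment, week 16 | 0.5^(3.68/2.6) = 37.5% | 0.5^(3.68/4.8) = 58.8% |
| Alive, week 8 | 83.3% | 90.6% |
| Alive, week 16 | 69.5% | 82.1% |

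At week 16, 62.5% v 41.2% are deteriorated with no form. Deaths make up 30.5 and 17.9 points. The remaining 32 and 23 points are living patients off treatment.

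**Step 2: the three-category test with no HRQoL difference in completers.** If a share π is on treatment, the class probabilities are 0.2π, 0.5π and 0.3π + 1 − π. At week 16 these are 0.075/0.187/0.738 (control) and 0.118/0.294/0.589 (ABT-414). The noncentrality is 80 × Σ[(a − p)² + (b − p)²]/p, where a and b are the arm probabilities and p is their mean. This gives about 4.0 on 2 df, a rejection probability of about 41%; 20,000 simulated trials agree.

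**Step 3: other readings.**

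| Reading | Week 8 | Week 16 |
|---|---|---|
| ITT rule, treatment stops at progression | 21% (17–27%) | 41% (34–50%) |
| ITT rule, progression found only at scans | about 9% | about 21% |
| SAP subset rule (at least one post-baseline form) | about 5–6% | about 15–16% |
| ITT rule, form given to all living patients | 8–9% | about 16% (13–20%) |
| ITT rule, equal PFS in both arms | – | 5% |

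Ranges cover the three completer splits. In the scan-only row, patients stay on treatment until the next visit, so the week 16 shares become 61.2% v 76.7% and the week 8 shares equal those alive. The subset row assumes that PFS and OS rank patients in the same order. The subset is then essentially those with a week 8 form, so week 8 is near nominal. Among them the week 16 on-treatment shares are 0.375/0.612 = 61% and 0.588/0.767 = 77%.

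**The case against.** Much of the case against stands.

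- **The subset rule matters.** If it governs, patients with no post-baseline form drop out and are not scored as deteriorated, and the effect is much smaller. But the later ITT sentence in SAP 10.3 says otherwise, and nothing shows which one prevails.
- **PFS is an imperfect stand-in for time on treatment.** The form is handed out before the doctor is seen (Protocol 10.4), so a patient whose progression is found at that scan can still complete it. Hence the scan-only row.
- **The model has no toxicity stops.** Its living off-treatment patients have all progressed. The documents give no rate of stopping without progression, so that group cannot be sized.
- **The plan has partial safeguards.** The CRF records why a form is missing, Protocol 10.5 plans a sensitivity analysis by that reason, and Protocol 10.5.1 examines the compliance mechanism. These can expose the problem but cannot recover forms that were never requested.
- **The stakes are limited.** HRQoL is exploratory and outside the fixed testing sequence, and Protocol 10.5 puts magnitude ahead of tests.

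A reader might also infer that compliance is capped at about 54% v 72% at week 16 (37.5/69.5 and 58.8/82.1), and that the schedule itself triggers the rule "In case overall compliance is deemed too low (<50%), only an exploratory analysis will be performed in lieu of the main analysis". The documents support neither. The cap reads time on study as time alive. The SAP does not define the term, and a progressed patient has no scheduled MRI visit to define T. The rule refers to overall compliance, which even on that reading is (37.5 + 2 × 58.8)/(69.5 + 2 × 82.1) ≈ 66% at week 16.

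**Conclusion.** The defect holds for the week 8 and week 16 three-category classification and for the compliance figures of patients who stop without progression. Whether a form is expected from a progressed patient is unclear. Under the ITT rule that patient is scored as deteriorated either way.

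On the stated assumptions, the week 16 chi-square rejects between about 15% and 50% of the time with no HRQoL difference in completers, depending on the population rule, how progression is detected and the completer split. At week 8 the range is from near nominal to 27%. Deaths account for part of this: giving the form to all living patients still leaves about 16% at week 16.

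It would go too far to say that the whole HRQoL comparison measures time on treatment. The 6-month form is collected on or off treatment, the change-from-baseline ANOVA in SAP 10.3 states no rule that counts missing as deteriorated, and the primary OS result is untouched. It is still worth correcting, because the week 8 and 16 classification cannot otherwise be read as an effect on global health.

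**What to change.** 1. In Protocol 10.4, 6.3.6 and footnote 8 (and SAP Table 1, footnote 8), offer the week 8 and 16 forms regardless of treatment status, at the MRI visit for every patient still being scanned. For progressed patients, use any visit already held in the window, such as the day-35 or day-49 visit.
2. In the SAP, count a form as expected only in patients who were to be asked for it, and define time on study.
3. For data collected under the on-treatment rule, report two categories separately from observed deterioration: off treatment with no form requested, and died. Keep missing counted as deteriorated as a sensitivity analysis.
4. In SAP 10.3, choose between the subset with a post-baseline form and the ITT population, and state one rule.

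Items 2 to 4 need only SAP wording. Item 1 adds a paper form at visits already held, so form handling rises slightly. Some progressed patients will still have no visit in the window.
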